## 2. List of study objectives

Primary objective is:

1. Baseline to 24-week Change in Liver Fat (measured by proton magnetic resonance spectroscopy,  $\Delta \%$ )

Secondary objectives are:

1. Baseline to 24-week Change in Body Composition including subcutaneous and visceral adipose tissue volume (measured by magnetic resonance imaging), total body fat and lean tissue mass (measured by Bioelectrical Impedance Analysis)
2. Baseline to 24-week Change in Liver Stiffness measured by transient elastography (Fibroscan ®)
3. Baseline to 24-week Change in Glucose Metabolism including fasting glucose, insulin, 2-h oral glucose tolerance test
4. Baseline to 24-week Change in Lipid Profile (LDL and HDL cholesterol, Triglyceride)
5. Baseline to 24-week Change in Metabolic and Inflammatory Biomarkers (e.g. high-sensitivity C-reactive protein (hsCRP), adiponectin, etc)
6. To collect subcutaneous adipose tissue samples at baseline and 24 weeks for future gene expression studies
7. To collect stool and saliva samples at baseline and 24 weeks for future microbiome studies
8. To collect safety and tolerability data related to the switch to raltegravir
9. Determination of the fatty liver adipose allele (B-PNPLA3)
10. Determination of basal metabolic rate by indirect calorimetry at screening and at the end of study

## 3. Study subjects

Actual subject recruitment will start after ethics committee (EC), competent authority (CA) and clinic approvals have been granted. The study subjects will be recruited and screened in a single center (Aurora hospital, Infectious diseases clinic, HUH, Helsinki). All the eligible study subject candidates will be contacted during regular visits and informed of the study by study investigators verbally and with a written information hand out. After adequate time and opportunity to inquire about details of the study and to decide whether or not to participate in the study, the candidates will sign and personally date an informed consent. After the study has finished, all the study subjects will continue their regular follow up with a chance to continue their current ART or to switch to another regimen.

The total number of study subjects included in the study is 45. Study subjects will be randomized 1:1 to continue current ART regimens or to switch their PI or efavirenz to once daily raltegravir

plus continue current NRTIs. The randomization will be stratified by age, sex and antiretroviral regimens (PI or efavirenz).

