## 6. Data analysis

The data will be analyzed by the investigators and the study group.

All variables of the data will be analyzed after the last subject's last visit, when the data have been declared complete.

The data will be analyzed using IBM SPSS Statistics v. 22. The differences between the groups will be analyzed by using chi-square, Fisher's exact, Mann-Whitney U test and others, as appropriate.

As there are no earlier ART-switch studies using H-Magnetic resonance spectroscopy for the quantification of liver fat, the calculation of the study power is an estimate. In the STERAL study evaluating the effect of switching from efavirenz (EFV) to RAL vs. continuing Efv-based ART, a statistically significant difference in the liver fat content using CAP (controlled attenuated parameter) was shown with a study sample of 19 +18 subjects after 48 weeks (7,3% decrease in the RAL vs. 11,0% increase in the Efv arm, p = 0,019) (11).

The power of this study is calculated with the assumption of liver fat being 4.4-5.0% in this study group at baseline. This estimation is based on our previous results published in 2002, when the median liver fat was 8% with lipodystrophic patients and 3% with non-lipodystrophic patients (17). Hadigan et al reported liver fat content being >5% in 42% of HIV positive subjects (18). As the liver fat content correlates with visceral fat mass, studying overweight or obese patients with at least one metabolic syndrome component includes patients at high risk for elevated liver fat content.

In the power calculation, we have used a coefficient of variation (CV) of H-Magnetic resonance spectroscopy being 11% (17). To detect a 9% difference between study arms with 80% power, a minimum sample size of 25 + 25 subjects with a 10% drop-out rate is needed.

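### Section 3 plans 45 subjects, section 6 requires at least 25 + 25, and 45 randomised with 10% drop-out misses the stated 80% power at two-sided 5%

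*Combined protocol and SAP*

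**What the plan says.** Section 3 (Study subjects) gives the planned size: "The total number of study subjects included in the study is 45". The next sentence begins "Study subjects will be randomized 1:1 to continue current ART regimens", the alternative being a switch to raltegravir. Section 4.1 adds that a subject who meets the criteria may enter the study and is randomised after consent. Nothing there describes 45 as a count of completers.

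Section 6 (Data analysis) holds the only sample-size justification. It uses a CV of 11% for the spectroscopy measurement and a baseline liver fat of 4.4-5.0%. For a target of 80% power and an arm difference of 9%, it concludes that "a minimum sample size of 25 + 25 subjects with a 10% drop-out rate is needed". It concedes that "the calculation of the study power is an estimate". No alpha, sidedness, scale or test is attached to the calculation. For group comparisons in general it names chi-square, Fisher's exact, "Mann-Whitney U test and others, as appropriate".

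**The concern.** A planned total of 45 cannot meet a stated minimum of 50. That conflict is on the face of the text and needs no assumption about alpha, scale or test.

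The number to randomise and the power for the primary objective are basic design figures for ethics and authority review. As written, the clinic cannot tell whether recruitment stops at 45 or at 50, and a reader could credit a 45-subject trial with 80% power. That matters most if the liver-fat comparison is not significant, because its interpretation then depends on what the trial could have detected.

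The drop-out wording adds a second ambiguity: 25 + 25 could be the number enrolled with the 10% loss already allowed for, or the number needed for analysis.

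**Working it through.** **Inputs from section 6:** difference 9%, CV 11%, power 80%, drop-out 10%. **From section 3:** 45 subjects, 1:1. **Assumed, because not stated:** two-sided 5%; the 9% is relative (baseline liver fat is only 4.4-5.0%); the 11% serves as the SD of the outcome.

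**Step 1. Reproduce 25 + 25.** With a constant SD the standardised difference is d = 9/11 = 0.818.

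- Normal approximation: n per arm = 2 × [(1.960 + 0.842)/d]² = 23.4, so 24.
- t-test: 24.4, so 25. This matches 25 + 25, but as the number analysed. Dividing by 0.9 gives 25/0.9 = 27.8, so 28 per arm randomised.
- Log scale, 9% decrease: SD = √ln(1 + 0.11²) = 0.1097 and d = −ln(0.91)/0.1097 = 0.860. The normal approximation needs 21.2, so 22 evaluable; 22/0.9 = 24.4, so 25 enrolled. This matches 25 + 25 as the number enrolled.

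Both readings give 25 per arm, so the text cannot settle whether drop-out is already included.

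**Step 2. The two totals.** 50 − 45 = 5 subjects short. 50 × 0.9 = 45. 45 × 0.9 = 40.5, or 20.25 per arm.

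**Step 3. Power at two-sided 5%.** The normal approximation is Φ(d√(n/2) − 1.960). For constant SD at n = 20.25 this is Φ(2.603 − 1.960) = Φ(0.643) = 74.0%. The t-test figures use the noncentral t distribution. "Proportional" below means that the SD scales with the arm mean.

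| Reading | d | 45 randomised, 10% lost: t-test | same, normal approx. | 45 evaluable (23/22): t-test |
|---|---|---|---|---|
| Constant SD | 0.818 | 71.8% | 74.0% | 76.5% |
| Proportional SD, 9% decrease | 0.856 | 75.6% | 77.7% | 80.1% |
| Proportional SD, 9% increase | 0.782 | 68.0% | 70.2% | 72.7% |
| Log scale, 9% decrease | 0.860 | 76.0% | 78.1% | 80.5% |
| Log scale, 9% increase | 0.786 | 68.4% | 70.6% | 73.1% |

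With whole subjects and constant SD, the t-test gives 71.3% at 20/20 and 72.4% at 21/20. The Mann-Whitney test gives 69.1% and 70.2% (20,000 simulated trials, normal data).

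**Step 4. Detectable difference at 80% power** (constant SD, t-test): 10.0% at 20/20, 9.9% at 21/20, 9.4% at 23/22 and 8.9% at 25/25.

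**The case against.** The strongest reply is that 45 means completers. On the log scale with a 9% decrease, 25 + 25 enrolled less 10% leaves 45 evaluable and power of 80.5% (t-test) or 82.2% (normal approximation). The design would then be coherent and only section 3 loosely worded. This is possible, but the plan states neither the log scale nor the completer meaning, and section 3 would still give the wrong number to randomise.

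Second, the shortfall depends on a two-sided 5% level that the plan does not state. At one-sided 5%, 45 randomised with 10% loss gives 81.9% by t-test (constant SD). That assumption needs only 19 to 20 evaluable per arm, or 22 to 23 with drop-out, so it does not reproduce 25 + 25. The power figures still have to carry the two-sided 5% condition.

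Third, the mismatch explains only part of the loss. With constant SD and the t-test, 50 analysed gives 80.9%, 50 randomised with 10% loss gives 76.5%, and 45 randomised with 10% loss gives 71.8%. About half of the fall comes from drop-out, so changing section 3 to 50 would not restore 80% on this reading. This stands.

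Fourth, section 6 describes the 11% as the CV of the measurement method, not the between-subject SD of a 24-week change. If that SD were 11 × √2 = 15.6 (an assumption), power would be about 45% with 45 randomised and 10% loss (normal approximation). This also stands: the percentages here illustrate the plan's own inputs and do not forecast actual power.

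Finally, the synopsis listed as an attachment is not in the text reviewed, so the absence of a reconciliation refers to the protocol text only.

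**Conclusion.** The concern holds. That 45 is below the plan's own minimum of 50, with no reconciliation, rests on no assumption. The size of the power loss does: at two-sided 5%, with a 9% difference, an 11% SD and 10% drop-out, 45 randomised gives about 72% (constant SD, t-test), with 68% to 78% across the scales and approximations tried, none reaching 80%. If 45 is the evaluable count, t-test power runs from 73% to 80.5% and meets the claim only for a 9% decrease on the proportional-SD or log scale. This must be corrected, because as written a reader cannot tell which number governs or whether the 80% applies to it.

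**What to change.** Amend sections 3 and 6 so that they give the same two numbers: subjects randomised, and subjects expected to be evaluable after 10% drop-out. State in section 6 the alpha, sidedness, scale and test behind the calculation.

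- If 45 means completers from 50 randomised, say so in section 3 and show that the stated inputs give 80% at 45 evaluable.
- If 45 is the number randomised, replace the 80% claim with what 45 delivers: about 72% power for a 9% difference, or 80% power for a difference of about 10%, on the constant-SD, two-sided 5% assumption.

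In either case recompute with the SD the plan finally adopts; the figures given here should not be copied in. The cost is about two sentences and a short recalculation. No extra subjects are needed if the power is restated, but restating it only makes the document consistent; it does not raise the power.

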**The inclusion criteria are:**

- Written informed consent (IC) obtained.
- HIV-positive adult (age over 18) subjects currently on stable ART, with no changes in the ART regimens during the past 6 months.
- Current ART includes either a protease inhibitor or efavirenz.
- No documented or suspected resistance to integrase inhibitors or to NRTIs.
- No prior history of virologic failure. Failure is defined as a confirmed plasma viral load  $> 200$  cop/ml measured no less than six months after initiation or modification of therapy.
- Virological blips accepted only if a single viral load measurement has been between 50-200 cop/ml followed by VL  $< 50$  cop/ml without the need to initiate a change in ART and no blip within 12 month window period prior to screening.
- Documented evidence of at least two HIV VL  $< 50$  cop/ml measurements during the past 12 months prior to inclusion: one within 6 months prior to screening.
- HIV VL  $< 50$  cop/ml at screening.
- $BMI > 25 \text{ kg/m}^2$  and one metabolic syndrome condition, which are
  - $BP \geq 130/\geq 85 \text{ mmHg}$  or hypertension medication currently in use or
  - fasting glucose  $\geq 5.6 \text{ mmol/l}$  or  $B\text{-HbA1C} > 42 \text{ mmol/mol}$  or diabetes medication currently in use or
  - $HDL < 1.0 \text{ mmol/l}$  in men and  $< 1.3 \text{ mmol/l}$  in women or triglycerides  $\geq 1.7 \text{ mmol/l}$  or a cholesterol-lowering regimen currently in use or
  - waist circumference  $> 94 \text{ cm}$  in men and  $> 80 \text{ cm}$  in women (or respective cut off values for non-European ethnic groups as defined by International Diabetes Federation).

OR

- ultrasound or biopsy proven hepatosteatosis.

**Exclusion criteria are:**

- Within 12 month window period prior to screening, HIV VL measurement of  $\geq 50$  cop/ml.
- More than one consecutive HIV VL measurements of  $\geq 50$  cop/ml in the treatment history after initial viral suppression with ART.
- Chronic hepatitis B or C.
- Daily alcohol consumption  $\geq 30 \text{ g}$  for men and  $\geq 20 \text{ g}$  for women.
- Pregnancy or planned pregnancy during the study period.

- Lipid or glucose lowering regimen or hormonal supplement started within 3 months before the planned study start.
- Psychiatric disorder, which prevents a study subject to understand the study protocol.
- Other serious disease, which prevents a study subject to participate in the study.
- For MRI/spectroscopy imaging: metal objects in the body or claustrophobia.

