### 4.1. Screening visit

A screening visit will be performed prior to first study visit in Obesity Research Unit. The screening visit consists of the following procedures:

- A physical examination will be performed and demographic data will be recorded including subject's gender, date of birth, ethnicity, substance use, recent and current alcohol use (AUDIT questionnaire), smoking status, weight, height, BMI, and waist and hip circumferences.
- Medical history and current medical conditions and concomitant treatments will be inquired and recorded.
- Blood pressure and heart rate will be measured.

The subject may enter into the study if all the inclusion criteria and none of the exclusion criteria are met and will be randomized to one of the treatment arms after signing the informed consent (IC). Recording of adverse events (AEs) starts from the time that a study subject signs the IC form. The study subjects will be given a study diary, where they can fill in AEs and possible concomitant treatments during the study. They will be asked to fill a dietary and exercise diary for three days at the study start and at the end of study.

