#### 4.3. Study procedures in the Obesity Research Unit and in the Radiology Department

The study protocol includes two visits in the Obesity Research Unit. The first visit will take place after randomization and before the switch of the ART. The second visit will take place after 24 weeks of follow up.

Study subjects are advised to fast 10-12 hours before each visit in the Obesity Research Unit (water is allowed during fasting). Alcohol intake is prohibited from 48 h before each study visit. Smoking is prohibited during the visits. Apart from these restrictions the subjects are advised to keep to their usual exercise and lifestyle habits for the duration of the study.

The visits consist of the following study measurements: Oral glucose tolerance test (OGTT), measurements of liver fat by 1H-spectroscopy, body composition by MRI, hepatic stiffness by transient elastography and calorimetry for measurement of basal metabolic rate. Samples of blood, urine, stool and saliva are collected, ECG and subcutaneous adipose tissue biopsies taken, and health questionnaire filled in.

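### The metabolic co-medication exclusion names only recent starts, not stops or dose changes, and changes after entry have no stated use in the analysis

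*Combined protocol and SAP*

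**What the plan says.** The only eligibility rule on the stability of metabolic co-medication is in the exclusion criteria of section 3: "Lipid or glucose lowering regimen or hormonal supplement started within 3 months before the planned study start". It names initiation and nothing else.

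The inclusion criteria of the same section admit treated patients. The glucose condition can be met by the alternative "or diabetes medication currently in use or", and the lipid condition by "a cholesterol-lowering regimen currently in use". For ART the wording is broader and longer: stable treatment "with no changes in the ART regimens during the past 6 months".

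On recording, section 4.1 states: "Medical history and current medical conditions and concomitant treatments will be inquired and recorded". It also gives subjects a diary "where they can fill in AEs and possible concomitant treatments during the study". Section 5.3 classes clinically important adverse events that lead to substantial added treatment as other significant AEs, and requires the investigator to document all AEs.

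On conduct after entry, section 4.3 deals with fasting, alcohol and smoking around visits and then says: "Apart from these restrictions the subjects are advised to keep to their usual exercise and lifestyle habits for the duration of the study". Medication is not mentioned. Section 4 leaves follow-up to standard of care in an open-label design.

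Section 6 lists group comparisons (chi-square, Fisher's exact, Mann-Whitney U and others). It says nothing on how co-medication changes enter the analysis.

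**The concern.** The primary objective (24-week change in liver fat) and secondary objectives 3 and 4 (glucose metabolism, lipid profile) are outcomes that lipid-lowering, glucose-lowering or hormonal treatment may move. The exclusion exists to keep a recent treatment change from showing up as a 24-week change, but a stop or a dose change can do that as well as a start. A subject whose cholesterol-lowering drug was stopped two weeks before study start is eligible as the criterion is written, provided the other criteria are met.

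After entry, changes are neither restricted nor given a place in the analysis. With about 22 subjects per arm, a few such subjects can widen the spread of the outcome noticeably. If they fall unevenly between arms, a reader of the results could not tell how much of a difference, or of its absence, to attribute to the ART switch.

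**Working it through.** **1. The two stability rules in section 3**

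| | ART | Lipid, glucose and hormonal drugs |
|---|---|---|
| Window | 6 months | 3 months |
| Starts | ruled out | ruled out |
| Stops | ruled out (any change) | not named |
| Dose changes | ruled out (any change) | not named |
| Current users eligible | yes | yes; use can itself meet a qualifying condition |

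The gap lies in the second column, in a population where treated patients are expected.

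**2. The plan's own power figure (section 6)**

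Inputs from section 6 are a 9% difference, an 11% coefficient of variation and 80% power. Two-sided alpha 0.05 is assumed, since none is stated. Using the 11% as the SD:

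n per arm = 2 × (1.960 + 0.842)² × 11² / 9² = 23.5, so 24. The t-test version gives 24.4, so 25.

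The stated 25 + 25 is thus reproduced, best as the number before drop-out (24 inflated for 10% loss is 27). Section 3 gives a total of 45, or 22.5 per arm on average; that difference from 25 + 25 is a separate matter. Power by normal approximation is 82% at 25 per arm and 78% at 22.5 per arm.

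**3. Noise from changes that are balanced between arms**

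The documents give neither the frequency nor the effect of such changes, so both are assumed. Let a fraction q of each arm have a change that shifts the 24-week result by d points on the scale of the 9% difference. Then SD = √(11² + q(1 − q)d²).

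| q | d | SD | Power, 22.5 per arm | Power, 25 per arm |
|---|---|---|---|---|
| 0 | any | 11.00 | 78% | 82% |
| 5% | 10 | √(121 + 4.75) = 11.21 | 77% | 81% |
| 10% | 20 | √(121 + 36) = 12.53 | 67% | 72% |
| 20% | 30 | √(121 + 144) = 16.28 | 46% | 50% |

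The last row needs 0.20 × 22.5 = 4.5 subjects per arm, each shifted by 30 points. The expected between-arm difference stays at 9 in every row.

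**4. Changes after randomisation that are unbalanced**

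If one arm has an excess fraction q of subjects whose results improve by d, the observed difference moves by q × d. Over the same non-zero assumptions this is 0.05 × 10 = 0.5 to 0.20 × 30 = 6.0 points. An excess in the control arm turns 9 into 8.5 to 3.0. An excess in the raltegravir arm turns it into 9.5 to 15.0. With no excess it stays at 9. The arithmetic does not give the sign, so the documents have to be searched for one.

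**5. Do the documents point to one direction?**

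- Towards more treatment in controls: section 1 reports lipids falling after a switch from a PI or efavirenz to raltegravir, and allocation is open.
- Against: Table 1 in section 4.2 has no lipid test between baseline and week 24, and glucose only at week 2. Scheduled tests would not show clinicians a lipid divergence between arms.
- Against: the baseline metabolic tests precede the switch (section 4.3), so abnormal baseline results are balanced in expectation.
- Towards more treatment in the raltegravir arm: section 5.2 lists raised triglycerides among the common adverse effects, and section 1 reports higher odds of severe weight gain on raltegravir, in ART-naive patients.

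No direction is established.

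**The case against.** The strongest reply has four parts.

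- *On-study changes are not unrecorded.* A reader might infer that nothing covers the 24 weeks. That is too strong. Co-treatments are recorded at screening, the diary takes them during the study, section 5.3 captures some through significant AEs, and AEs are asked about at weeks 2, 8 and 24. What remains is that diary entry is worded as optional, a drug begun for a pre-existing abnormality need not appear as an AE, and no use of the record is stated.
- *Pre-baseline changes do not bias the comparison.* This stands for changes made before randomisation, which 1:1 allocation balances in expectation. The cost is precision. Changes made after allocation, including any between screening and the baseline visit, lack that protection.
- *A started regimen may be read to include a newly altered one.* That is possible for a dose change, so part of the point is clarification. It does not reach a stop.
- *Under standard-of-care follow-up, a comparison that includes later co-treatment is a legitimate treatment-policy question.* This stands, and is why all randomised subjects should stay in the main analysis. It does not remove the need to show how much co-treatment each arm received.

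**Conclusion.** The point holds as a gap in one eligibility criterion and in the reporting plan. As written, the exclusion admits subjects with a recent stop or dose change in the drug classes it was written to control. This adds noise to the primary endpoint and to objectives 3 and 4. On assumed inputs from no effect to 20% of subjects shifted by 30 points, power with 45 subjects runs from 78% down to 46%. Where the trial lies in that range cannot be read from the documents. The figures also take the 11% measurement CV as the SD of the outcome, as the plan appears to do. If the true SD is larger, the same changes add proportionately less to it.

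A reader might go further and infer that controls will receive more new treatment, so that a real benefit of the switch is masked. The documents do not support a direction: no lipid result is scheduled between baseline and week 24, and they also give reasons for added treatment in the raltegravir arm. An imbalance after entry could hide or exaggerate the effect. Nor do the documents support stating any fixed share of the 9% difference as lost to co-treatment, because they give no frequency or drug effect on which to base it.

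**What to change.** 1. Reword the exclusion in section 3 so that it applies to a lipid- or glucose-lowering regimen or hormonal supplement *started, stopped or changed in dose within 3 months before the planned study start*. Cost: one reworded criterion, and a few candidates deferred by up to 3 months.
2. In section 6, state that all randomised subjects stay in the main analysis whatever co-medication changes follow. From the concomitant-treatment record already collected, report by arm the number who start, stop or change the dose of such a drug after baseline, as context for the primary endpoint and objectives 3 and 4. Cost: one descriptive table.

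Neither step restricts care during the trial; which treatments may be changed remains a clinical decision for the sponsor and investigators.

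A sensitivity analysis that sets values after a co-medication change to missing may look like a natural addition, but it is not recommended. Liver fat is measured only at baseline and week 24 (section 4), so it would delete the subject's only post-baseline value. That value would then have to be imputed essentially from baseline, conditional on a post-randomisation event, with about 22 subjects per arm.
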